4.2. Treatment Arms and Duration

The total duration of subject involvement is up to 16 weeks (Screening to Follow-up) as described below:

- Screening: Screening will occur at least one week prior to but not more than 30 days prior to washout.
- ESA Washout: Subjects that meet eligibility criteria will begin the 2-week ESA washout at Week -2.
 - This should be timed such that this day occurs on the date that would have been the next scheduled dose of ESA (or as close as practicable).
 - For subjects with a three-times weekly dialysis schedule, this day must not occur on the first dialysis session of the week (e.g., if Monday-Wednesday-Friday schedule, the study visit cannot be on Monday).
 - For subjects with a four- to five-times weekly dialysis schedule, this day can be on any hemodialysis session of the week.
- Randomization & Acute Challenge 1 (Day 1): Subjects will be randomized 1:1 to two treatment arms as described in [Table 1](#) and will begin a 24-hr Acute Challenge where the acute BP effects of daprodustat and epoetin alfa will be

evaluated. This challenge will be initiated promptly following the subject's dialysis session.

- **Hgb Maintenance Period:** Subjects randomized to daprodustat will start an 8-week Hgb maintenance period based on a starting dose and dose adjustment algorithm as described in Section 6.4.1. Subjects randomized to epoetin alfa will begin an 8-week Hgb maintenance period where Hgb will be managed in accordance with local labelling.
- **Acute Challenge 2:** At the end of the 8-week Hgb maintenance period, subjects will repeat the procedures of Acute Challenge 1 utilizing the same treatment administered in Acute Challenge 1. This challenge will be initiated promptly following the subject's dialysis session.
- **Follow-up:** A Follow-up visit will be scheduled to occur 14 ± 3 days after completing treatment.

Table 1 Treatment Arm Descriptions

Treatment Arm	Acute Challenge 1	Hgb Maintenance Phase	Acute Challenge 2
A	100 U/kg IV epoetin alfa	IV epoetin alfa according to label	100 U/kg IV epoetin alfa
B	24 mg daprodustat	QD daprodustat according to dose adjustment algorithm (Section 6.4.1)	24 mg daprodustat

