6.2. Treatment Assignment

Subjects will be stratified by prior ESA dose (as outlined in Section [4.1](#)) and randomized 1:1 to receive open-label oral daprodustat or IV epoetin alfa. A central randomization approach will be used due to the small sample size and to protect against potential selection bias due to the open-label design. Once a randomization number has been assigned by an Interactive Voice/Web Response System (IVWRS) at time of Randomization, it must not be re-assigned.

Subjects will be assigned to study medication in accordance with the randomization schedule generated by Clinical Statistics, prior to the start of the study, using validated internal software.

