### 11.3. Exploratory Pharmacodynamic and Biomarker Analyses

#### 11.3.1. Endpoint / Variables

Exploratory Objectives	Exploratory Endpoints

 
To investigate the effect of daprodustat and epoetin alfa on vasoactive mediators of blood pressure
 
	
 
Plasma concentrations and derived parameters including Cmax, tmax, and AUC(0-24) as appropriate (to include erythropoietin, endothelin-1, nitric oxide, asymmetric dimethylarginine, renin, angiotensin-II and metabolites, and noradrenalin)
 

CONFIDENTIAL

205665

Exploratory Objectives	Exploratory Endpoints

 
To summarize the effect of daprodustat and epoetin alfa on SBP after Acute Challenge 1 and Acute Challenge 2
 
	
 
AUEC of SBP as measured by ABPM over 24-hr post-dosing
 

 
To compare the effect of daprodustat to epoetin alfa on SBP after 8 weeks of Hgb maintenance therapy
 
	
 
Change from Day 1 pre-dose SBP to Day 57 pre-dose
 

 
To compare the effect of daprodustat to epoetin alfa on SBP at Cmax of the study treatment
 
	
 
Change in SBP from pre-dose on Day 1 to Cmax of the study treatment on Day 1, as measured by ABPM
 
Change in SBP from pre-dose on Day 1 to Cmax of the study treatment on Day 57, as measured by ABPM
 
Change in SBP from pre-dose on Day 57 to Cmax of the study treatment on Day 57, as measured by ABPM
 

 
To compare the effect of daprodustat to epoetin alfa on SBP at Cmax of the erythropoietin level
 
	
 
Change in SBP from pre-dose on Day 1 to Cmax of erythropoietin on Day 1, as measured by ABPM
 
Change in SBP from pre-dose on Day 1 to Cmax of erythropoietin on Day 57, as measured by ABPM
 
Change in SBP from pre-dose on Day 57 to Cmax of erythropoietin on Day 57, as measured by ABPM
 

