**CONFIDENTIAL**

205665

each acute challenge. Cmax, tmax, AUC(0-24), baseline adjusted AUC and baseline adjusted Cmax will all be summarized by treatment arm and for each acute challenge day.
 
 
• Change in AUEC of SBP from Day 57 to Day 1 for each treatment arm will be summarized in a table.
 
• The difference in SBP between pre-dose in Acute Challenge 1 and pre-dose in Acute Challenge 2 will be summarized by treatment group. Similar summaries of DBP, MAP, and HR will be performed.
 
• For each acute challenge, change from pre-challenge in SBP, DBP, MAP, and HR will be summarized by treatment group at each timepoint. In addition, for each acute challenge, SBP, DBP, MAP, and HR will be summarized by treatment group at each timepoint. Line graphs of this information will be provided by treatment group for each acute challenge.
 
• For the following endpoints, an ANCOVA model will be used with terms for baseline SBP, treatment, and prior ESA dose (low/high): 
 
○ Change in SBP from pre-dose on Day 1 to Cmax of the study treatment on Day 1, as measured by ABPM
 
○ Change in SBP from pre-dose on Day 57 to Cmax of the study treatment on Day 1, as measured by ABPM
 
○ Change in SBP from pre-dose on Day 57 to Cmax of the study treatment on Day 57, as measured by ABPM
 
○ Change in SBP from pre-dose on Day 1 to Cmax of erythropoietin on Day 1, as measured by ABPM
 
○ Change in SBP from pre-dose on Day 57 to Cmax of erythropoietin on Day 1, as measured by ABPM
 
○ Change in SBP from pre-dose on Day 57 to Cmax of erythropoietin on Day 57, as measured by ABPM
 
 
 

Model Checking & Diagnostics
 
 
• Distributional assumptions underlying the statistical analyses will be assessed by visual inspection of residual plots. Normality will be examined by normal probability plots, while homogeneity of variance will be assessed by plotting the residuals against the predicted values for the model. If assumptions are grossly violated, alternative analyses will be considered.
 

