
 
● Nitrate umol/L = Nitrite Total - Nitrite Endogenous 
 
○ The Nitrate concentration is an indirect method to estimate Nitric Oxide.
 
○ Nitric Oxide label will be used in place of nitrate concentration
 
 
 
● Geometric mean=exp (mean on loge scale)
 
● CVb (%)=SQRT(exp(SD**2)-1)x100, where SD is the standard deviation of the loge-transformed data.
 
● Natural Log-transformation, (Ln), of biomarker data will not be done for Tmax
 
● AUC(baseline corrected) = Calculated AUC - (baseline level*time) 
 
○ Where baseline level is defined as the pre-dose measurement for each visit
 
○ Where time is the last time measurement, for most subjects this would be 24 hours.
 
○ To be done on a by subject level then summarized by treatment for each visit
 
 
 
● Cmax(baseline corrected) = Cmax - baseline level 
 
○ Where baseline level is defined as the pre-dose measurement for each visit
 
○ To be done on a by subject level then summarized by treatment for each visit
 
 
 
	
Parameter	Parameter Description
AUC(0-24)	
Area under the concentration-time curve from time zero to the time of the last quantifiable concentration (C(t)) will be calculated using the linear trapezoidal rule for each incremental trapezoid and the log trapezoidal rule for each decremental trapezoid.
 
 
○ If subject is missing pre-dose or 24-hour data, then exclude from AUC calculation.
 

Cmax	Maximum observed plasma concentration, determined directly from the concentration-time data.

CONFIDENTIAL

205665

Pharmacodynamic and Biomarker					
Tmax	Time to reach Cmax, determined directly from the concentration-time data.				
Exploratory endpoints					

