
 
• For exploratory endpoints utilizing ANCOVA models:               
 
○ Baseline SBP data point will come from the SBP/DBP/HR/MAP reading recorded from the ABPM data. The zero time, first recorded measurement from the ABPM device, will be used as the post HD pre acute challenge variable as per the guidelines under ABPM data.                   
 
▪ If the data is missing from the ABPM data, the eCRF vital signs data will be used                       
 
• Post-dialysis measurement will be used
 
 
 
▪ If MAP variable is needed from eCRF, MAP will be calculated the following way:
 
▪ <math>MAP = (SBP + 2(DBP)) / 3</math>
 
 
 
○ Change from baseline will be defined as average of the BP from ABPM device, within <math>\pm 20</math> min from tmax, minus the baseline SBP data point.                   
 
▪ Discrete timepoints will be used
 
▪ If no ABPM data is available with the <math>\pm 20</math> min window, then the calculated average will be marked as “.” to indicate missing since no ABPM data is available within that window.
 
 
 
○ If repeat day 57 data is available, then the Cmax data will be based on the non-repeat visit and the ABPM data will be based on the repeated visit.
 
○ If more than one tmax is listed for a given cmax, only the first tmax will be used.
 
 
 
• For Daprodustat subjects, the tmax from treatment and the tmax from epoetin alfa data will be used
 
• For rEPO subjects, the tmax from epoetin alfa will be used for both endpoints analysing tmax of ABPM data.
 
					
Plot of ABPM Data					

 
• Hourly average of each of the four ABPM measurements (SBP, DBP, MAP, and HR) for AC1 and AC2 will be generated for each subject               
 
○ Hourly averages defined as follows:
 
 
 
					
Hour	Measurement 1	Measurement 2	Measurement 3	Measurement 4	Average
0-1	121	115	122	120	$(121+115+122+120)/4 = 119.5$
...					
5-6	121	115	122	Missing	$(121+115+122)/3 = 119.3$
6-7	121	115	122	No data possible	$(121+115+122)/3 = 119.3$
...					
23-24	120	121	missing	No data possible	$(120+121)/2=120.5$

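### The exploratory SBP-at-Cmax comparisons read the two arms at different post-dose times, so their estimates mix drug effect with the natural course of SBP after dialysis

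*SAP*

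**What the plan says.** SAP 11.3.1 lists two exploratory objectives of this kind, one at Cmax of the study treatment and one worded "To compare the effect of daprodustat to epoetin alfa on SBP at Cmax of the erythropoietin level". Each has three endpoints. SAP 14.6.6 (Exploratory endpoints) defines the outcome as the mean of the ABPM readings within 20 minutes either side of tmax, minus the pre-dose value. Tmax is observed per subject: "Time to reach Cmax, determined directly from the concentration-time data".

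The reading time differs by arm. In one arm, "For Daprodustat subjects, the tmax from treatment and the tmax from epoetin alfa data will be used". In the other, "For rEPO subjects, the tmax from epoetin alfa will be used for both endpoints analysing tmax of ABPM data". Protocol Table 4 takes drug PK samples only in the daprodustat arm, so the comparator's tmax has to come from the erythropoietin assay.

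For the analysis, SAP 11.3.1.1 says "an ANCOVA model will be used with terms for baseline SBP, treatment, and prior ESA dose (low/high"). A point estimate, 95% CI and p-value are presented from every such model. No term represents time since dose or since dialysis.

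Subjects are "randomized 1:1 to receive open-label oral daprodustat or IV epoetin alfa" (Protocol 6.2). On dose timing, Protocol 4.2 says "This challenge will be initiated promptly following the subject's dialysis session".

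**The concern.** Randomisation makes the arms comparable at the same post-dose time. It does not do so at different times that follow from which drug was given.

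Erythropoietin is sampled at 0.5, 1, 2, 3, 4, 6, 8, 12, 16 and 24 h after dosing. Intravenous epoetin, which that assay measures directly, should show its highest value at or near the first sample. Daprodustat must be absorbed, and the erythropoietin it induces must then be produced, so both peaks should come later and the second later still. This is inferred from route and mechanism; the documents state no tmax.

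Dosing follows dialysis closely, so hours after dose are roughly hours after dialysis, and 24 hours of monitoring includes a night. If SBP drifts over that period whatever the treatment, the drift between the two reading times enters the treatment coefficient. A night-time fall would flatter daprodustat, and a rise between dialysis sessions would count against it. Adjusting for pre-dose SBP removes neither. The bias does not shrink with sample size. At stake is the reading of six planned estimates and p-values.

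**Working it through.** **1. The mechanism.** Let m(t) be the natural SBP change from pre-dose at t hours, common to both arms, and let tD and tE be the reading times in the daprodustat and epoetin arms. The treatment coefficient then estimates

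drug difference + B, where B = m(tD) − m(tE), averaged over the observed tmax values.

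B is zero only if the arms share the same tmax distribution or m is flat over the gap. The epoetin tmax serves both sets of endpoints, so for the same challenge the epoetin readings are identical in the two sets. With no drug effect, those two results could differ systematically only through the times used for daprodustat.

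**2. The protocol's own figure.** Protocol 9.2.1 assumes 25 per arm, SD 16 mmHg and a 15 mmHg difference. SE = 16 × √(2/25) = 4.525. The half-width is 2.011 × 4.525 = 9.10 mmHg. Noncentrality is 15/4.525 = 3.31, and the two-sided t-test on 48 df has power 90.1%. Table 6 gives 90% and 9.1 mmHg, so the calculation reproduces it.

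**3. Rejection rate for a given B and no drug effect.** Inputs: 25 per arm; SD 14 to 20 mmHg (Protocol Table 7); residual df = 50 − 4 = 46; critical t = 2.013; noncentrality = B / (SD × √(2/25)). The table's SD is for the 6-hour mean SBP. Using it for a change read over a 40-minute window is an assumption.

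| SD | SE | B = 3 | B = 5 | B = 8 | B = 10 |
|---|---|---|---|---|---|
| 14 | 3.96 | 11.5% | 23.5% | 50.7% | 69.6% |
| 16 | 4.53 | 10.0% | 19.1% | 41.0% | 58.1% |
| 18 | 5.09 | 8.9% | 16.1% | 33.7% | 48.5% |
| 20 | 5.66 | 8.1% | 13.9% | 28.3% | 41.0% |

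At B = 0 every row is 5%.

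**4. The two sets of endpoints compared.** The SAP model was simulated with no drug effect, 25 per arm, SD 16 and 5,000 trials per case. Assumed times: epoetin at 0.5 h; daprodustat plasma tmax evenly 1, 2, 3 or 4 h (mean 2.5 h, gap 2 h); induced erythropoietin tmax 6, 8 or 12 h with weights 0.3, 0.4 and 0.3 (mean 1.8 + 3.2 + 3.6 = 8.6 h, gap 8.1 h). A linear drift common to both arms gives:

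| Drift (mmHg/h) | Study-treatment Cmax | Erythropoietin Cmax |
|---|---|---|
| 0 | 4.4% | 4.4% |
| 0.5 | 5.2% | 13.4% |
| 1 | 6.8% | 40.7% |
| 2 | 13.3% | 92.1% |

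The last row is an extreme case for erythropoietin, since 2 × 8.1 is about 16 mmHg. The contrast between the columns is the useful result: the same drift matters far more where the time gap is longer.

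**5. Matched times.** With both arms read at the same distribution of times and the 2 mmHg/h drift kept, rejection returns to 4.8% (study-treatment times) and 5.0% (erythropoietin times). The mean spurious difference is about 0.1 mmHg.

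**The case against.** **These tests decide nothing.** SAP 5.5 treats them as exploratory without Type I error control. The superiority rule in SAP 11.2.5.1 for the secondary models is not repeated in 11.3.1.1. This stands and limits the importance of the point. It does not cure the estimate, since an exploratory label addresses multiplicity and not bias.

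**Own-peak reading is what the protocol asks for.** Protocol section 3 defines the endpoints at Cmax of each study treatment and of erythropoietin. This also stands. The by-arm summary is legitimate; the defect lies in a between-arm test that is not matched on time.

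**Matched-time information is already planned.** Tables 4.21 to 4.24 give change from pre-dose by timepoint and arm, and Figures 4.1, 4.5 and 4.9 give hourly mean SBP. A reader could see a common trend there. What is missing is an estimated between-arm contrast at the relevant hours.

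**The size rests on assumptions.** This stands in full. The documents' text contains no tmax values and no SBP time course; Protocol Figure 2 concerns MAP in a published study, and its values are not in the text. Opposing trends can also offset each other. For the erythropoietin endpoints at SD 16, simulated night falls of 10 and 15 mmHg gave about 16-20% and 30-36% rejection, but only 6-15% once a 10 mmHg rise over 24 hours was added. The study-treatment tests stayed at about 5-12% under nearly all profiles tried, reaching 17% only with a 15 mmHg fall alone and a night starting at 22:00.

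A reader might infer that all six tests are badly inflated, or that they will favour daprodustat. The documents support neither inference: the two sets differ in exposure to the problem, and the direction depends on an SBP profile that is not given.

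**Conclusion.** The point holds for the exploratory between-arm inference in Tables 4.27 to 4.32. That the model confounds treatment with reading time follows from the SAP's definitions. That the arms' tmax values differ is an inference from route and sampling schedule. How far SBP moves naturally over the gap is unknown.

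The conditional size is therefore a range: about 8-12%, 14-24%, 28-51% or 41-70% rejection for a natural difference of 3, 5, 8 or 10 mmHg, assuming 25 per arm and SD 20 to 14 mmHg. These are not predicted error rates for this trial. The three erythropoietin-Cmax tests carry most of the risk.

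A reader might also infer that the trial's main blood pressure conclusion is compromised. It is not: the primary 6-hour mean and the secondary 6-hour means and 24-hour AUECs use the same window in both arms, and no success rule rests on the at-Cmax tests. The change is worth making because it is cheap and those tables would otherwise invite a causal reading.

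**What to change.** 1. Keep SBP at each subject's own Cmax as a by-arm descriptive summary, with no between-arm p-value, or with the comparison labelled as not time-matched.
2. For each challenge, fit a repeated-measures model to hourly change from pre-dose SBP with treatment, hour, treatment-by-hour, pre-dose SBP and prior ESA dose. Report the treatment difference and 95% CI at three hours: the median epoetin tmax, the median daprodustat plasma tmax and the median erythropoietin tmax in the daprodustat arm. Both arms are estimated at the same hour each time.
3. For the protocol's cross-day endpoints (Day 1 pre-dose to Cmax on Day 57), fit the same model to Day 57 hourly SBP minus Day 1 pre-dose SBP.
4. Reconcile the SAP with the protocol on the middle endpoint of each set. SAP 11.3.1.1 and Tables 4.28 and 4.31 run from Day 57 pre-dose to Cmax on Day 1; Protocol section 3 and SAP 11.3.1 run from Day 1 pre-dose to Cmax on Day 57.

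The cost is SAP wording and three models on data already collected; SAP 14.6.6 already derives hourly averages. A structured covariance should be named in advance, because an unstructured one for 24 hourly means has 24 × 25/2 = 300 parameters for about 50 subjects. The downsides are that contrasts sit at median tmax and not at each subject's own peak, and that three models at three hours give nine contrasts, still exploratory and unadjusted.

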## 14.7. Appendix 7: Reporting Standards for Missing Data

### 14.7.1. Premature Withdrawals

Element	Reporting Detail
General	
 
Participant study completion (i.e. as specified in the protocol) was defined as a participant who has completed all phases of the study including the follow-up visit.
 
Participants that withdraw prior to the Acute Challenge 2 assessment or subjects who do not pass QC for Acute Challenge 2 will be replaced so that 25 participants per treatment arm complete and pass QC for Acute Challenge 2.
 
All available data from participants who were withdrawn from the study will be listed and all available planned data will be included in summary tables and figures, unless otherwise specified.
 
Withdrawal visits will be slotted as per Appendix 3: Assessment Windows or will be summarised as withdrawal visits.
 

### 14.7.2. Handling of Missing Data

Element	Reporting Detail
General	
 
Missing data occurs when any requested data is not provided, leading to blank fields on the collection instrument: 
 
These data will be indicated by the use of a “blank” in participant listing displays. Unless all data for a specific visit are missing in which case the data is excluded from the table.
 
Answers such as “Not applicable” and “Not evaluable” are not considered to be missing data and should be displayed as such.
 
 
 

Outliers	
 
Any participants excluded from the summaries and/or statistical analyses will be documented along with the reason for exclusion in the clinical study report.
 

#### 14.7.2.1. Handling of Missing and Partial Dates

Element	Reporting Detail
General	
 
Partial dates will be displayed as captured in participant listing displays.
 

Adverse Events	
 
The eCRF allows for the possibility of partial dates (i.e., only month and year) to be recorded for AE start and end dates; that is, the day of the month may be missing. In such a case, the following conventions will be applied for calculating the time to onset and the duration of the event: 
 
Missing Start Day: First of the month will be used unless this is before the start date of study treatment; in this case the study treatment start date will be used and hence the event is considered On-treatment as per Appendix 4: Study Phases and Treatment Emergent Adverse Events.
 
Missing Stop Day: Last day of the month will be used, unless this is after the stop date of study treatment; in this case the study treatment stop date will be used.
 
 
 
Completely missing start or end dates will remain missing, with no imputation applied. Consequently, time to onset and duration of such events will be missing.
 

Concomitant Medications/ Medical History	
 
Partial dates for any concomitant medications recorded in the CRF will be imputed using the following convention: 
 
If the partial date is a start date, a '01' will be used for the day and 'Jan' will be used for the month
 
 
 

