7.3.1.1. Time Period and Frequency for Collecting AE and SAE Information

- Any SAEs assessed as related to study participation (e.g., protocol-mandated procedures, invasive tests, or change in existing therapy) or related to a GSK product will be recorded from the time a subject consents to participate in the study up to and including any follow-up contact.
- AEs will be collected from the start of washout until the follow-up contact (see Section 7.3.1.3), at the timepoints specified in the Time and Events Table (Section 7.1).
- Medical occurrences that begin prior to the start of washout but after obtaining informed consent may be recorded on the Medical History/Current Medical Conditions section of the CRF.
- All SAEs will be recorded and reported to GSK within 24 hours, as indicated in Section 12.4. The investigator will submit any updated SAE data to the sponsor within 24 hours of it being available.
- Investigators are not obligated to actively seek AEs or SAEs in former study subjects. However, if the investigator learns of any SAE, including a death, at any time after a subject has been discharged from the study, and he/she considers the event reasonably related to the study treatment or study participation, the investigator must promptly notify GSK.

NOTE: The method of recording, evaluating and assessing causality of AEs and SAEs plus procedures for completing and transmitting SAE reports to GSK are provided in Section 12.4.

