**14.4.2. Treatment Emergent Flag for Adverse Events**

All AEs (non-serious AEs and serious AEs) will be collected and recorded on the eCRF from the start of treatment, including washout period, until the follow-up visit at the time points specified in the SoA from [Appendix 2](#). Serious AEs assessed as related to study participation (e.g., study treatment, protocol-mandated procedures, invasive tests, or change in existing therapy) or related to a GSK product will be recorded on the eCRF from the time a participant consents to participate in the study up to and including any follow-up contact.

Treatment State	Definition
Pre-treatment	
 
For participants with a non-missing screen failure date, if AE onset is on or before the screen failure date: AE Start Date <math>\leq</math> Screen Failure Date
 
For randomized participants with a missing treatment start date, all AEs are considered pre-treatment
 
For randomized subjects with a non-missing treatment start date, if AE onset date is before treatment start date: AE Start Date <math><</math> Treatment Start Date
 

Post-randomization	If AE onset date or AE worsening date is on or after the randomization date Randomization date $\leq$ AE Start Date Randomization date $\leq$ AE Worsening Date
Treatment emergent	If AE onset date or AE worsening date is on or after treatment start date & on or before the last non-zero dose date plus 1 day. Treatment Start Date $\leq$ AE Start Date $\leq$ Last Non-Zero Dose Date + 1 day Treatment Start Date $\leq$ AE Worsening Date $\leq$ Last Non-Zero Dose Date + 1 day
Follow-up	If AE onset date or AE worsening date is after the last non-zero dose date plus 1 day. AE Start Date $>$ Last Non-Zero Dose Date + 1 day AE Worsening Date $>$ Last Non-Zero Dose Date + 1 day
Onset /Worsening Time Since 1 st Dose (Days)	If Treatment Start Date $>$ AE Onset Date = AE Onset Date - Treatment Start Date + 1 If Treatment Start Date $\leq$ AE Onset Date = AE Onset Date - Treatment Start Date + 1 If Treatment Start Date $>$ AE Worsening Date = AE Worsening Date - Treatment Start Date If Treatment Start Date $\leq$ AE Worsening Date = AE Worsening Date - Treatment Start Date + 1 Missing otherwise.

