Onset/Worsening Time Since Last Dose (Days)	If Last Non-Zero Dose Date $<$ AE onset date: AE onset date – last non-zero dose date If Last Non-Zero Dose Date $\geq$ AE onset date: AE onset date – last non-zero dose date If Last Non-Zero Dose Date $<$ AE worsening date: AE worsening date – last non-zero dose date If Last Non-Zero Dose Date $\geq$ AE worsening date: AE worsening date – last non-zero dose date Missing otherwise.
Duration (Days)	AE Resolution Date – AE Onset Date/AE Worsening Date + 1
Drug-related	If relationship is marked 'YES' on eCRF or if the value is missing.

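### The SAP's partial-date rules count some certainly pre-treatment adverse events as treatment-emergent and give negative durations to events that start after treatment stops

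*SAP*

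**What the plan says.** SAP 14.7.2.1 covers adverse events recorded with month and year only, and states that "the following conventions will be applied for calculating the time to onset and the duration of the event". Two of its rules matter here.

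- **Start day not recorded:** onset is placed on day 1 of the recorded month. Where that precedes treatment, the SAP adds that "in this case the study treatment start date will be used and hence the event is considered On-treatment". There is no condition that the recorded month be the month in which treatment started.
- **Stop day not recorded:** resolution is placed at the end of the recorded month, "unless this is after the stop date of study treatment; in this case the study treatment stop date will be used". There is no comparison with the onset date.

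SAP 14.4.2 computes duration as "AE Resolution Date – AE Onset Date/AE Worsening Date + 1". It classes an event in a treated participant as pre-treatment "if AE onset date is before treatment start date". It also defines a separate follow-up state for events starting more than one day after the last non-zero dose.

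Events can occur in both windows where these rules bite. Protocol 7.3.1.1 says "AEs will be collected from the start of washout until the follow-up contact", and Protocol 4.2 puts the follow-up visit 14 ± 3 days after treatment is completed.

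**The concern.** Imputing a missing day should not contradict what is known, and both rules can do so.

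The start rule overrides a recorded month that lies wholly before treatment. Incidence of adverse events is a stated safety endpoint (SAP 8). SAP 8.1 tabulates pre-treatment, treatment-emergent and follow-up events separately and splits on-treatment events by Acute Challenge 1, maintenance and Acute Challenge 2. A washout event moved to Day 1 would therefore appear as an event of the first single-dose challenge.

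The stop rule treats the end of treatment as the latest possible resolution date, although collection continues to follow-up. Derived durations then become impossible or too short.

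**Working it through.** The plan gives no figure to reproduce, so the check applies the rules as written. The example assumes Day 1 = 10 March 2019, which makes Day 57 = 5 May 2019. It takes the treatment stop date and the last non-zero dose date as both falling on Day 57.

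**Start rule**

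1. Onset is recorded as February 2019. The first of the month, 1 February, is before 10 March, so onset becomes 10 March.
2. The event now meets the treatment-emergent definition, although every day of February precedes treatment. SAP 14.4.2 would class any February date as pre-treatment.
3. If the event resolved on 4 March, duration = 4 − 10 + 1 = −5 days. If the stop is also recorded as February 2019, it becomes 28 February. That is 10 days before the imputed onset, so duration = −10 + 1 = −9 days.
4. With onset imputed within the recorded month (1 February), the event is pre-treatment. Resolution on 4 March is 31 days later, so duration = 31 + 1 = 32 days.

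**How often washout reaches an earlier month**

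This uses the SAP's average month of 30.4375 days. A washout of W days reaches the previous month when Day 1 falls on day 1 to W of its month. Onsets are assumed to be spread evenly over washout.

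| Washout | Day 1 dates reaching an earlier month | Onsets in an earlier month |
|---|---|---|
| 14 days (current) | 14/30.4375 = 46% | (1 + … + 14)/(14 × 30.4375) = 105/426.1 = 25% |
| 28 days (before Amendment 3) | 28/30.4375 = 92% | (1 + … + 28)/(28 × 30.4375) = 406/852.25 = 48% |

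Counting through every Day 1 date from 2017 to 2020 (an assumed range) gives the same shares. These are shares of washout events *whose start day is missing*, not of all washout events.

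**Effect of one event**

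Protocol 9.2.1 expects 31 randomized per arm, so one participant is 1/31 = 3.2%. That alone passes the 2% threshold for the common-event tables in SAP 8.1.

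**Stop rule**

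1. Let treatment stop on day T and the event start on day T + k, with the stop day missing. The recorded stop month cannot end before onset, so the cap always applies.
2. Duration = T − (T + k) + 1 = 1 − k. This is 0 for k = 1, −1 for k = 2, and −16 for k = 17, the latest day of the follow-up window. Every event starting at least 2 days after treatment stop gets a negative duration.
3. Day 60 onset: 57 − 60 + 1 = −2 days.
4. Dated example: onset 12 May, stop recorded as May 2019. The stop becomes 5 May, so duration = 5 − 12 + 1 = −6 days. Without the cap it is 31 − 12 + 1 = 20 days.
5. An event that starts on treatment and ends after it keeps a positive duration but is cut at treatment stop whenever the recorded stop month ends later than that.

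**The case against.** Much can be said for the plan.

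- **AESI durations.** A reader might infer that these are wrong. SAP 8.2 leaves AESI time to onset and duration missing when a date is incomplete, so the imputed values do not enter those summaries. This stands. But 8.2 and 14.7.2.1 give different instructions for the same dates without saying which prevails, and 8.2 does not correct the treatment-emergent flag.
- **Duration is not an endpoint.** The safety endpoints are incidence and severity, reasons for discontinuation, and laboratory, ECG and vital-sign values. No listed adverse event table is titled as a duration table, and listings show partial dates as recorded. This also stands: the stop rule has no demonstrated effect on a planned summary outside the AESI section.
- **Every partial date in washout or follow-up.** A reader might infer that all such events are mishandled. They are not. When the recorded month is the month of treatment start, the true date is ambiguous and assigning Day 1 is an accepted cautious convention. A washout event missing only its stop day is unaffected if that month ends by treatment stop. A follow-up event missing only its start day does not trigger the move to treatment start.
- **Direction.** The start rule over-counts, which is the cautious direction for a single arm's rate. Washout precedes randomization, so the excess should be similar in both arms. That makes bias between arms unlikely, but pre-treatment events still dilute the comparison.
- **Existing safeguard.** A note in SAP 14.4.2 classes an event as pre-treatment when onset is missing and resolution precedes treatment. It speaks of a missing onset. A partial onset has its own rule in 14.7.2.1, which states the on-treatment result outright.

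**Conclusion.** Both rules are wrong as written, within limits.

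The start rule misclassifies events whose recorded onset month ended before the month of treatment start. It contradicts the SAP's own pre-treatment definition and can inflate treatment-emergent incidence, a stated safety endpoint.

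The stop rule gives negative durations to events starting at least 2 days after treatment stop and shortens on-treatment events that continue into follow-up. Its reach is derived durations other than the AESI summaries.

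The conclusion rests on a literal reading of 14.7.2.1. The 25% and 48% shares also assume evenly spread onsets. The documents do not say how many partial dates to expect; the number is likely small. The primary SBP analysis is unaffected. This is a minor point, worth correcting because the correction is cheap.

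**What to change.** Make three edits before database freeze.

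1. **Missing start day:** use the treatment start date only when the recorded month and year are those of treatment start. Otherwise impute within the recorded month, and class the event as pre-treatment if that month precedes treatment start.
2. **Missing stop day:** remove the cap at treatment stop. Use the last day of the recorded month, never earlier than onset. Any upper limit should be the last date on which the event was followed. The SAP's last study contact date could be too early, because Protocol 7.3.1.3 follows SAEs and AESIs to resolution or stabilization.
3. **AESI rule:** cross-reference SAP 8.2 and 14.7.2.1 and state which governs AESI time to onset and duration.

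The cost is a few sentences in the SAP and a small change to the date-derivation code. No new data are needed.
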